4.5.6 Endometrial Thickness Assessment

To assess for any potential effect of study treatment on the uterus, transvaginal ultrasound scans will be performed to monitor endometrial thickness at screening, at the study drug discontinuation visit, and as clinically indicated. *Transvaginal ultrasounds are not required for patients who have had a hysterectomy.*

4.5.7 Electrocardiograms

An electrocardiogram (ECG; 12-lead) is required at screening and at the study drug discontinuation visit, and may be repeated during the study as clinically indicated.

All ECG recordings should be performed using a standard high-quality, high-fidelity digital electrocardiograph machine equipped with computer-based interval measurements. Lead placement should be as consistent as possible. ECG recordings must be performed after the patient has been resting in a supine position for at least 10 minutes. All ECGs are to be obtained prior to other procedures scheduled at that same time (e.g., vital sign measurements, blood draws) and should not be obtained within 3 hours after any meal. Circumstances that may induce changes in heart rate, including environmental distractions (e.g., television, radio, conversation) should be avoided during the pre-ECG resting period and during ECG recording.

For safety monitoring purposes, the investigator must review, sign, and date all ECG tracings. Paper copies of ECG tracings will be kept as part of the patient's permanent study file at the site.

If at a particular postdose timepoint the mean QTcF is > 500 ms and/or > 60 ms longer than the baseline value, another ECG must be recorded, ideally within the next 5 minutes, and ECG monitoring should continue until QTcF has stabilized on two successive ECGs. An unscheduled PK sample should be obtained, and the Medical Monitor should be notified. Standard-of-care treatment may be instituted per the discretion of the investigator. A decision on study drug discontinuation should be made, as described in Section 5.1.5. The investigator should also evaluate the patient for potential concurrent risk factors (e.g., electrolyte abnormalities, co-medications known to prolong the QT interval, severe bradycardia).

Clinically significant abnormalities observed during screening will be recorded on the General Medical History and Baseline Conditions eCRF. New or worsened clinically significant abnormalities and/or QTcF prolongations that meet the criteria described above will be recorded on the Adverse Event eCRF.

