4.5.11.3 Study Drug Discontinuation Visit

All patients who are discontinued from study drug will return for a study drug discontinuation visit within 30 days after the last dose of study treatment. The treatment completion visit procedures and assessments should be performed after permanent discontinuation of study drug. The visit at which disease progression is recorded may serve as the study drug discontinuation visit, provided that all tests required at the study drug discontinuation visit are performed. Assessment of disease progression based on clinical examination must be confirmed by radiographic assessment prior to or at the study drug discontinuation visit and before initiating new anti-cancer therapy.

Refer to the Study Flowchart in [Appendix 1](#) and [Appendix 2](#) for the schedule of assessments to be performed at the study drug discontinuation visit.

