5.3.1 Adverse Event Reporting Period

Investigators will seek information on adverse events at each patient contact. All adverse events, whether reported by the patient or noted by study personnel, will be recorded in the patient's medical record and on the Adverse Event eCRF.

After informed consent has been obtained **but prior to initiation of study drug**, only serious adverse events caused by a protocol-mandated intervention (e.g., invasive procedures such as biopsies, discontinuation of medications) should be reported (see Section 5.4.2 for instructions for reporting serious adverse events).

After initiation of study drug, all adverse events will be reported until 28 days after the last dose of study drug. After this period, the investigator should report any serious adverse events that are believed to be related to prior study drug treatment (see Section 5.6).

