Appendix 1 Schedule of Assessments for Patients on Arm A (GDC-0810)

	Screening ^a	Cycle 1		Cycle 2	Cycle 3	Cycle 4	Cycles 5+	Study Drug Discontinuation ^b
Day (Window)	-28 to -1	1	15 (+1) ^c	1 (+1) ^c	1 (±1) ^c	1 (±3) ^c	1 (±3) ^c	Within 30 days after last dose
Informed consent ^d	x							
Medical history and demographic data ^e	x							
Concomitant medications ^f	x	x	x	x	x	x	x ^g	x
Adverse events ^h	x	x	x	x	x	x	x ^g	x
Vital signs ⁱ	x	x	x	x	x	x	x	x
Complete physical examination, height, weight ^j	x							
Limited physical examination ^k		x	x	x	x	x	x	x
ECOG performance status	x	x	x	x	x	x	x	x
Single 12-lead ECG	x	As clinically indicated						x
Endometrial thickness assessment ^l	x	As clinically indicated						x
Tumor assessment ^m	x	x ^g						x
Bone scan ⁿ	x	x ^g						
Drug accountability		x	x	x	x	x	x	x
CBC with differential ^o	x	x	x	x	x	x	x ^g	x
Coagulation (INR, aPTT) ^p	x	As clinically indicated (see footnote)						
Blood chemistry ^q	x ^q	x	x	x	x	x	x ^g	x
FSH and estradiol	x ^r							
Urinalysis ^s	x	As clinically indicated						

Appendix 1
Schedule of Assessments for Patients on Arm A (GDC-0810) (cont.)

	Screening ^a	Cycle 1		Cycle 2	Cycle 3	Cycle 4	Cycles 5+	Study Drug Discontinuation ^b
Day (Window)	-28 to -1	1	15 (+1) ^c	1 (+1) ^c	1 (±1) ^c	1 (±3) ^c	1 (±3) ^c	Within 30 days after last dose
Archival (or fresh) FFPE tumor tissue ^t	x							
Plasma sample for ctDNA and plasma biomarkers ^u		x			x		x	x
Plasma sample for potential CDx ^v		x			x			
Plasma sample for PK analysis ^w		x			x			
Blood sample for pharmacogenetics ^x		x						
Optional blood sample for WGS ^y		x						
Optional tumor biopsy at progression ^z								x
GDC-0810 administration ^{aa}		x	x	x	x	x	x	

Appendix 1

Schedule of Assessments for Patients on Arm A (GDC-0810) (cont.)

aPTT=activated partial thromboplastin time; CBC=complete blood count; CDx=companion diagnostic; CT=computed tomography; ECG=electrocardiogram; ECOG=Eastern Cooperative Oncology Group; eCRF=electronic Case Report Form; EORTC=European Organization for Research and Cancer; FFPE=formalin-fixed, paraffin-embedded; FSH=follicle stimulating hormone; INR=international normalized ratio; PK=pharmacokinetic; PRO=patient-reported outcome; TSQM=Treatment Satisfaction Questionnaire for Medication; q12=every 12 (weeks); QLQ-BR23=Quality Of Life Questionnaire Breast Cancer Module; QLQ-C30=Quality Of Life Questionnaire; WGS=whole genome sequencing.

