Appendix 2 Schedule of Assessments for Patients on Arm B (Fulvestrant)

	Screening ^a	Cycle 1		Cycle 2	Cycle 3	Cycle 4	Cycles 5+	Study Drug Discontinuation ^b	
Day (Window)	-28 to -1	1	15 (+1) ^c	1 (+1) ^c	1 (±1) ^c	1 (±3) ^c	1 (±3) ^c	Within 30 days after last dose	
Informed consent ^d	x								
Medical history and demographic data ^e	x								
Concomitant medications ^f	x	x	x	x	x	x	x	x	
Adverse events ^g	x	x	x	x	x	x	x	x	
Vital signs ^h	x	x	x	x	x	x	x	x	
Complete physical examination, height, weight ^j	x								
Limited physical examination ^k		x	x	x	x	x	x	x	
ECOG performance status	x	x	x	x	x	x	x	x	
Single 12-lead ECG	x	As clinically indicated							
Endometrial thickness assessment ^l	x	As clinically indicated							x
Tumor assessment ^m	x	x^{i, n}							x
Bone scan ⁿ	x	Per clinical indication ⁿ							
CBC with differential ^o	x	x	x	x	x	x	xⁱ	x	
Coagulation (INR, aPTT) ^p	x	As clinically indicated (see footnote)							
Blood chemistry ^q	x^q	x	x	x	x	x	xⁱ	x^q	
FSH and estradiol ^r	x^r								
Urinalysis ^s	x	As clinically indicated							
Archival (or fresh) FFPE tumor tissue ^t	x								

Appendix 2
Schedule of Assessments for Patients on Arm B (Fulvestrant) (cont.)

	Screening ^a	Cycle 1		Cycle 2	Cycle 3	Cycle 4	Cycles 5+	Study Drug Discontinuation ^b
Day (Window)	-28 to -1	1	15 (+1) ^c	1 (+1) ^c	1 (±1) ^c	1 (±3) ^c	1 (±3) ^c	Within 30 days after last dose
Plasma sample for ctDNA and plasma biomarkers ^u		x			x		x	x
Plasma sample for potential CDx ^v		x			x			
Optional blood sample for WGS ^w		x						
Optional tumor biopsy at progression ^x								x
Fulvestrant administration ^y		x	x	x	x	x	x	

Appendix 2

Schedule of Assessments for Patients on Arm B (Fulvestrant) (cont.)

aPTT=activated partial thromboplastin time; CBC=complete blood count; CDx=companion diagnostic; CT=computed tomography; ECG=electrocardiogram; ECOG=Eastern Cooperative Oncology Group; eCRF=electronic Case Report Form; EORTC=European Organization for Research and Cancer; FFPE=formalin-fixed, paraffin-embedded; FSH=follicle stimulating hormone; INR=international normalized ratio; PK=pharmacokinetic; PRO=patient-reported outcome; q12=every 12 (weeks); QLQ-BR23=Quality Of Life Questionnaire Breast Cancer Module; QLQ-C30=Quality of Life Questionnaire; TSQM=Treatment Satisfaction Questionnaire for Medication; WGS =whole genome sequencing.

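### The discontinuation-visit ECG required by Section 4.5.7 is scheduled for Arm A but not for Arm B, so the only scheduled post-baseline ECG differs between arms in the appendices

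*Combined protocol and SAP*

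**What the plan says.** Section 4.5.7 states that a 12-lead ECG "is required at screening and at the study drug discontinuation visit, and may be repeated during the study as clinically indicated". It names no arm.

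The two schedules differ:

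- Appendix 1 (Arm A, GDC-0810) reads "Single 12-lead ECG x As clinically indicated x", with the last mark in the discontinuation column.
- Appendix 2 (Arm B, fulvestrant) reads "Single 12-lead ECG x As clinically indicated", with nothing after it.

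Section 4.5.11.3 refers sites to both appendices "for the schedule of assessments to be performed at the study drug discontinuation visit".

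On recording, Section 4.5.7 provides that "New or worsened clinically significant abnormalities and/or QTcF prolongations that meet the criteria described above will be recorded on the Adverse Event eCRF". Section 6.5 summarizes adverse events by treatment arm, and the safety objective in Section 2.2 compares GDC-0810 with fulvestrant.

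**The concern.** Two parts of the protocol give different instructions for the same visit in Arm B. The difference affects practice because Section 4.5.11.3 makes the appendices the working list for that visit. It also allows the progression visit to stand in for the discontinuation visit only if every required test is done, so sites need to know which tests are required.

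The statistical issue is ascertainment. A QTcF change or other ECG abnormality without symptoms is found only if someone records an ECG. If the one routine post-baseline ECG is done in Arm A and omitted in Arm B, such findings reach the adverse event tables more often for GDC-0810 even if the two drugs have the same effect on the ECG. Section 6.5 lists no ECG summary, so nothing in the planned output would show how many patients in each arm had the ECG.

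**Working it through.** No sample size, power or error rate is involved. The check sets the passages side by side and counts scheduled ECGs.

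**Step 1. Scheduled ECGs per patient after baseline**

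| Source | Arm A | Arm B |
|---|---|---|
| Section 4.5.7 | 1 (discontinuation) | 1 (discontinuation) |
| Appendix 1 / Appendix 2 | 1 (discontinuation) | 0 |
| Clinically indicated ECGs, all sources | allowed | allowed |

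Neither schedule fixes any ECG between screening and discontinuation, so the discontinuation ECG is the only scheduled post-baseline one. The scheduled difference is 1 − 1 = 0 by Section 4.5.7 and 1 − 0 = 1 by the appendices.

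**Step 2. Is the blank cell credible?** In the text as supplied, Appendix 2 carries an extra trailing column. The endometrial and tumor assessment rows, which also have a merged middle cell, show their discontinuation mark one cell further right than ordinary rows do. Those marks were displaced but not lost. The ECG row has no mark in either position, and it ends as the urinalysis row does, which has no discontinuation mark in either appendix. This favors a genuine omission but does not prove it.

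**Step 3. Do findings at this ECG enter the safety data?** The visit falls within 30 days after the last dose (Section 4.5.11.3). Adverse events are reported until 28 days after the last dose (Section 5.3.1). A visit by day 28 is therefore inside the reporting period; one on day 29 or 30 is not, apart from serious events believed related to study drug.

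**Step 4. Direction and bounds.** Let p be the probability that a routine discontinuation ECG yields a reportable finding that would otherwise be missed, taken as equal in both arms. Let c_A and c_B be the proportions of patients who have that ECG. The artificial difference in the proportion of patients with such an event is

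p × (c_A − c_B).

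- If all sites follow Section 4.5.7, c_B = c_A and the difference is 0.
- If all sites follow the appendices, c_B = 0 and the difference is p × c_A.

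Whenever c_A exceeds c_B, the sign is against GDC-0810. The documents give none of p, c_A or c_B, nor the number of patients enrolled per arm, so no event count follows.

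**The case against.** The strongest reply is that this is one table cell, read from a table that was visibly disturbed at the rows in question, while the body text already covers Arm B. Clinically indicated ECGs are allowed in both arms, and Section 5.3.1 adds that "Investigators will seek information on adverse events at each patient contact". The QTcF trigger in Section 4.5.7 refers to a postdose timepoint, which fits poorly with a visit up to 30 days after the last dose. QT prolongation is not among the identified or potential GDC-0810 risks in Sections 5.1.3 and 5.1.4. Section 6.5 plans no QTcF analysis, and Section 6.1 calls the study hypothesis-generating.

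Much of this stands. The blank cell needs checking, and the consequence is limited. It does not remove the contradiction: sites are sent to the appendices, and asking patients how they feel does not detect a silent ECG change. The postdose wording limits the QTcF trigger only; the recording rule also covers other new or worsened clinically significant abnormalities.

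A reader might infer three stronger things that the documents do not support:

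- That ECG adverse events are sought in one arm only. Section 4.5.7 read alone covers both arms, and clinically indicated ECGs remain open to both.
- That a planned comparison of QTcF change lacks a control value. The plan proposes no such comparison.
- That the excess can be counted, for example as 76 patients per arm (152 / 2) times an assumed yield of 2% to 5%, giving 1.5 to 3.8 events. The yield has no source in the documents, and 76 is a planning figure from before enrollment stopped. The product also assumes that every Arm A patient and no Arm B patient has the ECG.

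**Conclusion.** The inconsistency holds, subject to confirming the blank Appendix 2 cell against the original table. Its measurable size is 1 versus 0 scheduled post-baseline ECGs per patient under the appendices, against 1 versus 1 under Section 4.5.7. The consequence is possible unequal detection of clinically silent ECG findings, tilted against GDC-0810, in adverse event tables that serve a comparative safety objective. The direction assumes equal drug effects and that at least some Arm B sites followed Appendix 2; the number of events cannot be derived. Nothing suggests that unequal ECG monitoring was intended, and the documents do not settle which passage should prevail. This is a modest point that is cheap to correct. It is still live because Section 3.1 lets patients with clinical benefit stay on treatment, so discontinuation visits are still to come.

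**What to change.** 1. Check the Appendix 2 ECG row in the original table. If the cell is blank there, reconcile Section 4.5.7, Appendix 1 and Appendix 2 so that the ECG requirement at the discontinuation visit is stated consistently. Which version applies is for the sponsor to decide.
2. In the safety report, give the number of patients in each arm who had a discontinuation ECG, out of those who discontinued study drug.
3. Flag adverse events detected only at that ECG. Keep every event in the main adverse event tables, and show the between-arm comparison without the flagged events only as a supplement. Dropping them from the main comparison would remove safety events mostly from the investigational arm and could introduce a bias of its own.

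The cost is one schedule cell or one sentence, one line of counts and one flag in the adverse event listing. For patients already off treatment, only items 2 and 3 can help.

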4.5.8 Patient-Reported Outcomes

With the initiation of protocol amendment version 2, patient-reported outcomes will no longer be collected.

The EORTC QLQ-C30, QLQ-BR23, and a modified version of the TSQM will be collected to more fully characterize the clinical profile of GDC-0810 and fulvestrant.

The EORTC QLQ-C30 (see [Appendix 4](#)) and the QLQ-BR23 (see [Appendix 5](#)) are validated and reliable self-report measures ([Aaronson et al. 1993](#); [Sprangers et al. 1996](#); [Osoba et al. 1997](#)). The EORTC QLQ-C30 (version 3) consists of 30 questions that assess the following: global health status/HRQoL, five aspects of patient functioning (physical, emotional, role, cognitive, and social); three symptom scales (fatigue, nausea and vomiting, and pain); and six single items (dyspnea, insomnia, appetite loss, constipation, diarrhea, and financial difficulties) with a recall period of “the last week.” The EORTC QLQ-BR23 breast cancer module also uses a recall period of “the past

week,” and consists of 23 additional items assessing disease/treatment symptoms (systemic therapy side effects, breast symptoms, arm symptoms, and hair loss) and aspects of patient functioning (body image, sexual functioning, and future perspective).

The modified version of the TSQM (see [Appendix 6](#)) is a validated instrument consisting of 11 questions that measure patients’ satisfaction with medication. The 11 items incorporate 3 domains: side effects, convenience, and global satisfaction. The original version of the TSQM also contains a three-item subscale of effectiveness of treatment. The original TSQM had not previously been used in a cancer population, and during a validation study, cancer patients clearly indicated that they were not able to interpret or respond to the items on the effectiveness subscale.

The PRO instruments will be translated as required in the local language and completed in their entirety by the patient. To ensure instrument validity and that data standards meet health authority requirements, PRO questionnaires scheduled for administration during a clinic visit must be completed by the patient at the investigational site at the start of the clinic visit prior to other study assessments and before administration of study treatment. Interviewer assessment is allowed, but can only be conducted by a member of the clinic staff, if the patient is unable to complete the measure on their own. Study personnel should review all questionnaires for completeness before the patient leaves the investigational site.

An electronic PRO (ePRO) data collection modality will be employed. To capture PRO data during study treatment, patients will complete the questionnaires on a validated ePRO tablet at the site. The ePRO device and instructions for completing the PRO questionnaires electronically will be provided by the investigator staff. The data will be transmitted via a pre-specified transmission method (e.g., Web or wireless) automatically after entry to a centralized database at the ePRO vendor. The data can be accessed securely by appropriate study personnel via the Internet.

Please see [Appendix 1](#) for the schedule of PRO assessments. It should take approximately 10 minutes to complete the PRO assessments at each timepoint.

4.5.9 Laboratory, Biomarker, and Other Biological Samples

Samples for the following laboratory tests will be sent to the study site's local laboratory for analysis (see [Appendix 1](#) and [Appendix 2](#) for the collection schedule):

- Hematology: red blood cell count, hemoglobin, hematocrit, white blood cell count with differential (neutrophils, bands, eosinophils, basophils, lymphocytes, and monocytes), and platelet count
Reporting the differential as absolute counts is preferred, but percent is accepted
- Coagulation: aPTT and INR

- Serum or plasma chemistry: glucose, blood urea nitrogen or urea, creatinine, sodium, potassium, chloride, magnesium, bicarbonate, calcium, total protein, albumin, total bilirubin, ALP, AST, and ALT
- Urinalysis (macro): specific gravity, pH, glucose, protein, ketones, and blood, with reflex microscopic analysis done if macro is abnormal

[figure not shown]
Samples for the following laboratory tests will be sent to one or several central laboratories or to the Sponsor for analysis (see [Appendix 1](#), [Appendix 2](#), and [Appendix 3](#) for the collection schedule):

- Plasma samples for ctDNA isolation for exploratory research on candidate biomarkers, including but not limited to the following: *ESR1* mutations, *PIK3CA* mutations, and *AKT1* mutations
- Plasma sample to be banked for potential, future blood-based companion diagnostic development
- Plasma samples for PK analysis
- Blood for pharmacogenetic assessment (where approved by local regulatory authorities)
- Archival or newly collected (fresh) tumor tissue samples for *DNA and/or RNA extraction for exploratory NGS or other* research on candidate biomarkers, including but not limited to the following: *ESR1* mutation status, *PIK3CA* mutation status, ER/PgR and HER2 expression, LumA/B subtype, Ki67 IHC assay, and other assessments related to ER and PI3K signaling pathways

Sites must confirm the availability of a representative FFPE tumor specimen before initiating screening procedures.

In the event that multiple tissue blocks are available for a given patient (e.g., primary tumor and metastatic site), the most recently collected tumor sample must be submitted; both primary and metastatic tissue should be submitted where possible.

Tumor blocks are preferred, but in the event that local regulations prevent the shipment of tumor blocks, 10 unstained, serially cut, 5- μ M thick slides are requested (15–20 slides are preferred). Minimum tissue requirements are further described in the laboratory manual. Cytological, fine-needle aspiration, and bone biopsy samples are not acceptable.

- 
- If available, fresh tumor tissue samples collected at the time of disease progression
Tissue collection at the time of disease progression is not required for study participation. The tissue specimen will be requested for those patients who sign the Optional Research Informed Consent, and will be used for *DNA and/or RNA extraction* for exploratory research on mechanisms of resistance, including but not limited to the following: *ESR1* mutation status, *PIK3CA* mutation status, and other assessments related to ER and PI3K signaling pathways.
 - Optional blood sample for whole genome sequencing using an appropriate next-generation sequencing (NGS) platform

Laboratory manuals and supply kits will be provided for all central laboratory assessments. For detailed sampling procedures, storage conditions, and shipment instructions, see the laboratory manual.

Data arising from clinical genotyping will be subject to the confidentiality standards described in Section 8.4.

4.5.10 Assay Methods

4.5.10.1 Mutational Analysis for *ESR1*

Somatic mutations in the LBD of the *ESR1* gene confer ligand independence and are found in approximately 40% of metastatic breast cancers but are rare in primary breast cancers. ctDNA obtained from plasma offers a robust mutation detection alternative to tissue that can be collected with less inconvenience and risk to patients, particularly those with bone metastases that are difficult to biopsy. Quantitative real-time PCR (qRT-PCR) assays or NGS assays designed to interrogate the LBD of *ESR1* offer a sensitive and quantitative method to detect mutations from ctDNA. DNA will be extracted from plasma samples and subjected to NGS and/or qRT-PCR assays that detect the wild-type allele, as well as mutations that include, but are not limited to, the following amino acid changes: D538(G), Y537(S, N, C), E380(Q), L536(Q, H, P, R), S463P and P535H. Assays may also be run on metastatic tumor tissue if such tissue is available. Assays from all samples will be run in a central laboratory on analytically validated NGS and/or qRT-PCR platforms, and mutation calls will be made using appropriate cutoffs and automated software. The information about the spectrum and the prevalence of *ESR1* mutations may help with the development of a companion diagnostic for GDC-0810.

